16.1.3. Primary Analysis of Primary Efficacy Variables

The following hypotheses (H_{01} and H_{02}) for the coprimary endpoints will be tested:

H_{01} : The proportion of subjects achieving clinical remission at Week 12 is the same between etrasimod and placebo.

H_{11} : The proportion of subjects achieving clinical remission at Week 12 is different between etrasimod and placebo.

H_{02} : The proportion of subjects achieving clinical remission at Week 52 is the same between etrasimod and placebo.

H_{12} : The proportion of subjects achieving clinical remission at Week 52 is different between etrasimod and placebo.

Both hypotheses will be tested at the 2-sided α level, 0.05.

The primary efficacy analysis will be performed for the FAS with Baseline MMS 5 to 9. The Cochran-Mantel-Haenszel (CMH) test will be used, stratified by naïve to biologic or JAK inhibitor therapy at study entry (Yes or No), Baseline corticosteroid use (Yes or No), and Baseline disease activity (MMS: 4 to 6 or 7 to 9). Reported randomization stratum will be used in the model. Results will be expressed as the number and percentage of subjects in remission, difference in remission percentages and 95% CI and p-value, odds ratio and 95% CI. If there are no responders in both treatment groups in any stratum, the difference in remission percentages and associated inferences can still be made. However, the odds ratio and its CI may be calculated from the unstratified CMH.

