16.1.4.1. Multiple Imputation Under MAR

Any missing component scores of MMS at the planned assessments will be imputed using multiple imputation under MAR. MAR assumes the missing value is independent of unobserved outcomes given observed data (eg, subjects with missing RB subscores can be modeled based on subjects with observed RB subscores) (Rubin 1987).

The following steps will be implemented:

Step 1

Regardless of the arbitrary missing data pattern (ie, non-monotone or monotone), a fully conditional specification (FCS) method with predictive mean matching for continuous variables will be used to impute the missing data at all timepoints. The FCS method allows for separate conditional distributions for each imputed variable. The predictive mean matching approach creates a regression model using parameters sampled from the posterior distribution and then a predicted value for each missing value is computed. The missing value is replaced by randomly selecting an observation from a set of 'k' values that are the closest predicted values to the missing predicted value. Missing data imputation will be performed using the SAS PROC MI procedure. The number of imputations will be 40 and is based on a projected overall dropout rate of 50% and relative efficiency of ~ 99%. A separate imputation model will be used for each treatment group. The RB subscore, SF subscore, ES, PGA, stratification variables, a binary variable indicating if a subject is a prior UC treatment failure of oral 5-ASA only (ie, subject had an inadequate response, loss of response, or intolerance to previous treatment with oral 5-ASA and did not have an inadequate response, loss of response, or intolerance to any other previous UC medication), Geboes index score, and biomarker measurements (absolute lymphocyte count [ALC], fecal calprotectin [FCP], hs-CRP, log-transformed) at each planned visit will be included in the imputation models. Refer to [Appendix 3](#) for the order of variables and timepoints in the model.

Step 2

For each of the imputed datasets at Week 12 and Week 52, subjects will be classified as responder or nonresponder based on the criteria specified in Section 16. For each dataset, the proportion of responders will be calculated. For endpoints requiring MMS, MMS will be recomputed by summing the scores of ES, SF, and RB.

Step 3

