The CMH test, stratified by naïve to biologic or JAK inhibitor therapy at study entry (Yes or No), Baseline corticosteroid use (Yes or No), and Baseline disease activity (MMS: 4 to 6 or 7 to 9) will be run for each of the 40 datasets to obtain 40 estimators of interest at Week 12 and Week 52.

Step 4

Use SAS PROC MIANALYZE to produce an overall pooled estimate (mean of 40 estimates) with its associated standard error (SE), CI and pooled p-value.

However, there could be certain adjustments due to unexpected data issues after unblinding treatment. All post-unblinding modifications to the multiple imputation model or approaches to address missing data will be described in the CSR.

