16.1.4.2. Tipping Point Analysis

A tipping point approach based on multiple imputation of values through Week 12 and Week 52 will be used with a specified adjustment (referred to as delta adjustment or shift) applied to values imputed under a MNAR-based imputation model. To find a tipping point, a series of imputations will be performed with increasing values of delta.

The goal is to evaluate the plausibility of the assumed expected values for missing outcomes on each treatment group under which the conclusions change, ie, under which values of delta there are no longer evidence of significant treatment difference.

The following steps will be implemented:

Step 1

Same as Step 1 described in Section [16.1.4.1](#).

Step 2

Impute missing RB, SF, and ES subscores, then apply a random shift under the MNAR assumption to the imputed subscores and rounded to the nearest integer at Week 12 and Week 52 in both treatment groups, so that the expected value of the additive shift in RB, SF, and ES subscores combined is delta. The same variables used in Step 1 will be used in the MNAR model. The tipping point analysis sample code is specified in [Appendix 3](#). After the shift, if any assessments have values less than 0, the value will be set to 0. Similarly, if any assessments have values greater than 3, the value will be set to 3. MMS will then be rederived for each of the 40 imputed datasets, using the shifted values. Next, classify subjects as a responder or nonresponder at Week 12 and Week 52 based on the criteria specified in Clinical Study Protocol APD334-301 Section 10.5. For each dataset, the proportion of responders and nonresponders will be calculated.

Step 3

Same as Step 3 described in Section 16.1.4.1.

Step 4

Same as Step 4 described in Section 16.1.4.1.

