Note: Imputations with delta adjustment will be performed with progressively increasing delta values until a tipping point is reached based on the significance of the CMH test. A tipping point will correspond to the smallest value of delta for which the primary hypotheses are no longer rejected. The shift parameter (delta) for the etrasimod treatment group will take increasing values from 0 with increments of 1 (maximum MMS of 9) at the MMS level, representing adjustments towards worse outcomes (ie, after dropout, on average, subjects on treatment will have MMS worsen). For the placebo arm, delta adjustments will decrease with increments of 1, representing adjustments in the direction of better outcomes. The adjustments in each treatment group will be continued until the CMH test for the primary hypotheses are no longer significant at the 2-sided α level, 0.05. The corresponding shift parameters in both treatment groups at the tipping point will be reported along with the proportions and p-values from each CMH test.

Results will be plotted as a heat map on a two-dimensional plot with axes corresponding to the delta values used in each treatment group respectively, and different colors will be used to represent the magnitude of the 2-sided p-values corresponding to analysis with each combination of delta values. The clinical interpretation about the plausibility of the assumptions underlying the tipping point will be provided in the CSR.

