16.1.4.3. Multiple Imputation with Copy Reference

Missing data will also be explored assuming an MNAR approach. MNAR assumes the missing values depend on unobserved outcomes even after accounting for the observed data. Therefore, subjects cannot be modelled based on subjects with observed data, and more assumptions are needed. Copy reference is a type of MNAR approach where each missing value for subjects in the treatment group will be imputed using observed data in the placebo group, and missing values for subjects in the placebo group will be imputed under the MAR approach.

The following steps will be implemented:

Step 1**Step 1 (a)**

Intermittent missing data (before discontinuation from study) at each scheduled visit will be imputed, separately for each treatment group, under the MAR assumption using a multivariate normal imputation model and the Markov Chain Monte Carlo (MCMC) method with multiple chains. The number of imputations will be 40. The resulting data will have a monotone missing data pattern. The imputed data will be used together with the observed data to impute postdiscontinuation missing values.

Step 1 (b)

Only after Step 1a is completed, the remaining monotone missing data after discontinuation will be imputed using the FCS predictive mean matching method based on data from the placebo group only. The RB, SF, ES, and PGA subscores, stratification variables, a binary variable indicating if a subject is a treatment failure, and biomarker measurements (ALC, FCP, hs-CRP, log-transformed) at each planned visit will be included in the imputation model.

Step 2

Same as Step 2 described in Section 16.1.4.1.

Step 3

Same as Step 3 described in Section 16.1.4.1.

Step 4

Same as Step 4 described in Section 16.1.4.1.

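### Forty imputations meet the SAP's relative-efficiency target but do not control the Monte Carlo error of the pooled p-values, which matters mainly for the tipping point boundary

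*SAP*

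**What the plan says.** For the MAR analysis, SAP 16.1.4.1 (Step 1) sets the constant and gives its only stated basis: "The number of imputations will be 40 and is based on a projected overall dropout rate of 50" percent, together with a relative efficiency of about 99%. Step 4 pools by Rubin's rules: "Use SAS PROC MIANALYZE to produce an overall pooled estimate (mean of 40 estimates) with its associated standard error (SE), CI and pooled p-value".

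The tipping point analysis takes over the same imputation step and constant (16.1.4.2, Step 2): "MMS will then be rederived for each of the 40 imputed datasets, using the shifted values". The etrasimod shift "will take increasing values from 0 with increments of 1 (maximum MMS of 9) at the MMS level", and the placebo shift runs the other way. The result is then read off by a significance cut: "A tipping point will correspond to the smallest value of delta for which the primary hypotheses are no longer rejected". The level is two-sided 0.05. Copy Reference repeats the constant (16.1.4.3, Step 1a): "The number of imputations will be 40". The COVID-19 hybrid (16.1.4.4) inherits it by referring back to 16.1.4.1.

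The readable text sets no target for the Monte Carlo error of the p-value, the standard error or the boundary. Appendix 3, which holds the model order and the tipping point sample code, is redacted.

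**The concern.** Relative efficiency compares the variance of the pooled estimate under a finite number of imputations with its variance under an unlimited number. A pooled p-value needs more than that. It also depends on the between-imputation variance, which is itself estimated from only 40 values. A number of imputations that is ample for the estimate can therefore leave the p-value noisy.

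For a single pooled test this matters only if the answer lies near 0.05. The tipping point differs, because it is defined as the place where significance is lost, so it is always read off in the region where seed noise can change a verdict. The clinical study report is to interpret how plausible that tipping point is. The reported location should reflect the data and the assumed shifts, and as little as possible the seed.

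**Working it through.** **Inputs.** Number of imputations M = 40 and dropout 50% (SAP 16.1.4.1); two-sided 0.05 (16.1.3); 280 and 140 subjects, Week 52 rates 23.5% and 10.0% (SAP 7). The fraction of missing information, f, is not given. I assume 0.1 to 0.5, where 0.5 is the value implied by the SAP's own efficiency figure.

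**1. The SAP's figure.** RE = 1/(1 + f/M) = 1/(1 + 0.5/40) = 0.988. The stated figure of about 99% is reproduced.

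**2. Seed-to-seed SD of the pooled z.** Scale the total variance to 1, so that the between-imputation variance is f.
- From the estimate: √(f/M) = √(0.5/40) = 0.112.
- From the standard error: z × 0.5 × f × √(2/(M−1)) = 1.96 × 0.25 × √(2/39) = 0.111.
- Together: √(0.112² + 0.111²) = 0.158.

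A limiting z of 1.96 is then reported between 1.96 − 1.96 × 0.158 = 1.65 and 1.96 + 1.96 × 0.158 = 2.27, that is, p between about 0.099 and 0.023. With M = 200 the SD is 0.070.

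**3. The same by simulation** (pooled estimate normal, between-imputation variance scaled chi-square, Rubin degrees of freedom, at least 200,000 draws per setting). Middle 95% of the reported p when the limiting p is 0.05:

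| f | M = 40 | M = 200 | M = 1000 |
|---|---|---|---|
| 0.5 | 0.024 to 0.099 | 0.036 to 0.069 | 0.043 to 0.058 |
| 0.2 | 0.034 to 0.073 | 0.042 to 0.059 | 0.046 to 0.054 |
| 0.1 | 0.039 to 0.064 | 0.045 to 0.056 | 0.048 to 0.053 |

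**4. How near 0.05 must the limiting p be?** At f = 0.5 and M = 40, a limiting p of 0.04 is reported as non-significant for 33% of seeds, 0.03 for 13%, 0.02 for 2% and 0.01 for under 0.1%. For a limiting p of 0.04, the share falls to 10% with 200 imputations and 0.2% with 1000. At f = 0.2 the three shares are 15%, 0.7% and 0%.

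**5. At the design effect.** Week 52: z = 0.135/√(0.235 × 0.765/280 + 0.10 × 0.90/140) = 3.77. With f = 0.5 this becomes 3.77 × √0.5 = 2.66, p about 0.008. Simulating the pooling at the design rates with half the data missing gives a seed range of 0.003 to 0.027 at M = 40, with about 0.05% of seeds above 0.05.

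**6. Tipping grid, illustrative only.** Simulated 280:140 trials at the design rates, a 10 × 10 grid of shifts, six data sets, 30 seeds each (12 for M = 1000). The subscore distribution and the shift mechanism are my assumptions. Data sets with at least one cell whose verdict changed with the seed, and the number of such cells out of 100:

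| Missing / known nonresponse | M = 40 | M = 200 | M = 1000 |
|---|---|---|---|
| 50% / 0% | 4 of 6 (1 to 3 cells) | 3 of 6 (1 to 2) | none |
| 25% / 25% | 4 of 6 (1 to 9) | 3 of 6 (1) | none |
| 10% / 40% | 5 of 6 (1 to 16) | 3 of 6 (1 to 8) | none |

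In the first row the tipping delta at M = 40 moved by one step, once by two. In the other two it occasionally moved much further, where p is flat near 0.05.

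**The case against.** The strongest reply is that nothing decisive rests on these analyses. The primary method is nonresponder imputation (16.1.2), and that result alone opens the key secondary families (Table 3, note a). Choosing M by relative efficiency is a stated and correctly computed criterion, and no figure in the documents says how much Monte Carlo error is tolerable. All of this stands.

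A reader might also infer that the MAR, Copy Reference and hybrid conclusions would generally depend on the seed at 50% dropout. The documents do not support that, for three reasons.
- The 50% is projected dropout, not missing information. Under 16.1.2, discontinuation for worsening, lack of efficacy or a UC-related adverse event, and rescue, are known nonresponse. The repeated scores and biomarkers in the imputation model should lower the fraction further.
- At the design rates the MAR verdict is stable (step 5). Data sets built to sit near 0.05 are not cases of a positive trial losing its support. With 28/140 versus 7/70 responders observed and half the data missing, the pooled p ranges from 0.021 to 0.101 over seeds, but nonresponder imputation (28/280 versus 7/140, unstratified) already gives p = 0.081. With 40/210 versus 11/105 observed, the range is 0.020 to 0.061 and nonresponder imputation gives 0.057. With 44/238 versus 12/119, where nonresponder imputation succeeds (p = 0.042), the range of 0.017 to 0.039 never crosses 0.05.
- The hybrid imputes only endoscopy missing because of COVID-19, so its missing information should be small.

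Nor can the plan be said to lack a fixed seed or shared draws, because Appendix 3 is redacted and may specify both. The order of steps in 16.1.4.2 can be read as one set of imputations that is then shifted.

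On the tipping point, the SAP reports p-values, proportions and a heat map, not only a cut, and that softens the issue. With steps of one MMS point, p may also jump past 0.05 between neighbouring cells, so a given grid need not contain an unstable one. What remains is that the reported tipping delta is still defined by the cut, and cells near it can change.

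**Conclusion.** The point holds as a cheap improvement to the sensitivity analyses, not as an error in the plan. The 40 is consistent with its stated criterion, but the criterion does not govern the quantity by which the tipping point is read. Cells close to the boundary, not the whole grid, can change verdict with the seed, and this persists at a missing information fraction as low as 0.1. The MAR and Copy Reference verdicts are exposed only in the narrow band of limiting p given by step 4.

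The p-value ranges depend only on M and the assumed fraction of missing information. The cell counts rest on an assumed scoring and shift model and are illustrative. A fixed seed would make a result repeatable without making it less arbitrary. That has some weight here, because 16.1.4.1 allows the imputation approach to be modified after unblinding.

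**What to change.** In SAP 16.1.4.1 to 16.1.4.3, replace 40 by at least 200 imputations. Go higher, for example to 1000, if the Monte Carlo error of a p-value near 0.05 is still material; step 6 shows that 200 reduces boundary changes but does not remove them. The hybrid follows 16.1.4.1 by cross-reference and needs no separate figure. Report the Monte Carlo error of the pooled estimate and of the pooled p-value next to each result. Confirm, in Appendix 3 or the main text, that the seed is fixed before unblinding and that all tipping-grid cells use the same imputed draws, so that neighbouring cells differ only by delta.

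The cost is a changed constant in the SAP and code, plus computing time. A full 10 × 10 grid goes from at most 100 × 40 = 4,000 stratified tests to 100 × 200 = 20,000, or 100,000 with 1000 imputations. No new data are needed, and the primary analysis and alpha are unchanged.

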16.1.4.2. Tipping Point Analysis

A tipping point approach based on multiple imputation of values through Week 12 and Week 52 will be used with a specified adjustment (referred to as delta adjustment or shift) applied to values imputed under a MNAR-based imputation model. To find a tipping point, a series of imputations will be performed with increasing values of delta.

The goal is to evaluate the plausibility of the assumed expected values for missing outcomes on each treatment group under which the conclusions change, ie, under which values of delta there are no longer evidence of significant treatment difference.

The following steps will be implemented:

Step 1

Same as Step 1 described in Section [16.1.4.1](#).

Step 2

Impute missing RB, SF, and ES subscores, then apply a random shift under the MNAR assumption to the imputed subscores and rounded to the nearest integer at Week 12 and Week 52 in both treatment groups, so that the expected value of the additive shift in RB, SF, and ES subscores combined is delta. The same variables used in Step 1 will be used in the MNAR model. The tipping point analysis sample code is specified in [Appendix 3](#). After the shift, if any assessments have values less than 0, the value will be set to 0. Similarly, if any assessments have values greater than 3, the value will be set to 3. MMS will then be rederived for each of the 40 imputed datasets, using the shifted values. Next, classify subjects as a responder or nonresponder at Week 12 and Week 52 based on the criteria specified in Clinical Study Protocol APD334-301 Section 10.5. For each dataset, the proportion of responders and nonresponders will be calculated.

Step 3

Same as Step 3 described in Section 16.1.4.1.

Step 4

Same as Step 4 described in Section 16.1.4.1.

Note: Imputations with delta adjustment will be performed with progressively increasing delta values until a tipping point is reached based on the significance of the CMH test. A tipping point will correspond to the smallest value of delta for which the primary hypotheses are no longer rejected. The shift parameter (delta) for the etrasimod treatment group will take increasing values from 0 with increments of 1 (maximum MMS of 9) at the MMS level, representing adjustments towards worse outcomes (ie, after dropout, on average, subjects on treatment will have MMS worsen). For the placebo arm, delta adjustments will decrease with increments of 1, representing adjustments in the direction of better outcomes. The adjustments in each treatment group will be continued until the CMH test for the primary hypotheses are no longer significant at the 2-sided α level, 0.05. The corresponding shift parameters in both treatment groups at the tipping point will be reported along with the proportions and p-values from each CMH test.

Results will be plotted as a heat map on a two-dimensional plot with axes corresponding to the delta values used in each treatment group respectively, and different colors will be used to represent the magnitude of the 2-sided p-values corresponding to analysis with each combination of delta values. The clinical interpretation about the plausibility of the assumptions underlying the tipping point will be provided in the CSR.

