- An assumption of data missing at random (MAR) within each treatment group will be investigated. Missing data, eg, component scores of MMS at the planned assessment timepoints, will be imputed using multiple imputation methodology ([Rubin 1987](#)) under the MAR assumption. Binary responder-type endpoints will subsequently be computed from observed and imputed data and analyzed using the same method as in the primary analysis. Continuous endpoints will be analyzed using analysis of covariance based on observed and imputed values.
- A tipping point analysis will be performed for the primary and key secondary endpoints by considering all possible combinations of the number of responders and nonresponders among subjects with missing data in each treatment group. The results of analysis for all possible combinations will be summarized graphically, depicting a boundary between combinations that result in a statistically significant treatment effect versus not statistically significant. Clinical plausibility of the combinations on the boundary will be discussed in the clinical study report to evaluate robustness of study conclusions to missing data.
- A mechanism of missingness not at random will be investigated for subjects with missing data. These subjects, regardless of the randomized treatment group, will be assumed to have a similar distribution of outcomes after discontinuation as subjects with available data in the placebo group. This is akin to modeling the missing outcomes as if the subjects continued on their background therapy only and accounting for the study effect observed in subjects on placebo. This will be implemented using a multiple imputation approach of Copy Reference to impute missing values, eg, component scores of MMS at the planned assessment timepoints.

Complete descriptions of the sensitivity analyses and detailed multiple imputation method and procedures will be provided in the SAP prior to database lock.

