7. DETERMINATION OF SAMPLE SIZE

Based on a 2-group Fisher’s exact test, a 1-sided significance level of 0.025, and a 2:1 randomization ratio, 420 total subjects (280 etrasimod, 140 placebo) are required to achieve 93.4% power to detect a difference of 13.5% in the primary endpoint of clinical remission at Week 52 between the etrasimod treatment group (23.5%) and the placebo treatment group (10.0%). With this sample size, there will be 96% power to detect a difference of 12.5% in the other primary endpoint of clinical remission at Week 12, assuming a placebo rate at 6.0%. The lower bound of overall power for both primary endpoints (as coprimary endpoints), is at least 90%; since the 2 primary endpoints are expected to be at least moderately, positively correlated, the actual overall power to reject both of their null hypotheses is likely to be greater than 90%. Workbook calculations from EAST® 6 statistical software are included below.

Design: Discrete Endpoint: Two-Sample Test - Parallel Design - Fisher's Exact

Test Parameters	
Design ID	Week 52 Clin Rem
Test Type	2-Sided
Specified α	0.05
Power	0.934
Sample Size (n)	420
Model Parameters	
Proportion Treatment (π_t)	0.235
Proportion Control (π_c)	0.1
$\delta = \pi_t - \pi_c$	
Under H0	0
Under H1	0.135
Allocation Ratio (n_t/n_c)	2

Sample Size Information

Sample Size (n)	420
Treatment (n _t)	280
Control (n _c)	140

Design: Discrete Endpoint: Two-Sample Test - Parallel Design - Fisher's Exact

Test Parameters	
Design ID	Week 12 Clin Rem
Test Type	2-Sided
Specified α	0.05
Power	0.96
Sample Size (n)	420
Model Parameters	
Proportion Treatment (π_t)	0.185
Proportion Control (π_c)	0.06
$\delta = \pi_t - \pi_c$	
Under H0	0
Under H1	0.125
Allocation Ratio (n_t/n_c)	2

⊖ **Sample Size Information**

Sample Size (n)	420
Treatment (n _t)	280
Control (n _c)	140

8. STATISTICAL CONSIDERATIONS**8.1. Multicenter Studies**

This study will be conducted by multiple investigators at multiple centers internationally. Randomization to treatment groups is stratified by:

- Naïve to biologic or JAK inhibitor therapy at study entry (Yes or No)
- Baseline corticosteroid use (Yes or No)
- Baseline disease activity (MMS: 4 to 6 or 7 to 9)

Data from all sites will be pooled and statistical analyses will not be adjusted for investigational site, country, or geographic region.

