16.2. Key Secondary Efficacy

Key secondary efficacy endpoints are defined in Section 16. In general, all the primary and supplementary analyses planned for the primary endpoints in Section 16.1.3 and Section 16.1.4.4 will be repeated for each key secondary efficacy endpoint (Table 3). Additionally, the sensitivity analyses planned for the primary endpoints in Section 16.1.4 will be repeated for key secondary endpoints of endoscopic improvements and symptomatic remission (Table 3). Multiplicity adjustments for the family of the key secondary endpoints are discussed in Section 8.4.

Table 3: Planned Analyses by Endpoint

Endpoint	Primary Analysis of Stratified CMH	Sensitivity Analyses of MI, Tipping Point Analysis, MI with CR, and NRI + MI	Supplementary Analyses in mFAS and Per Protocol Set
Primary endpoints	X ^a	X	X
Key secondary endpoints:			
Endoscopic improvement	X	X	X
Symptomatic remission	X	X (MI, Tipping Point Analysis, and MI with CR only) ^b	X
Corticosteroid-free clinical remission	X		X
Mucosal healing	X	X (MI, MI-CR, and NRI + MI only)	X
Sustained clinical remission	X		X

^a Inference from the primary analysis method on the primary endpoints will be the gatekeeper for testing in the families of key secondary endpoints as per Section 8.4.

^b The hybrid missing data handling approach of NRI + MI will not be applied to the symptomatic remission endpoint since COVID 19 pandemic is not expected to impact subject eDiary entries.

Analyses in the table will be repeated for subjects in the specified analysis population with Baseline MMS 4 to 9. CMH, Cochran-Mantel-Haenszel; CR, copy reference; mFAS, modified full analysis set; MI, multiple imputation; NRI, nonresponder imputation.

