16.2.4. Sensitivity Analysis of Key Secondary Efficacy Variables

For the key secondary endpoints of endoscopic improvement, symptomatic remission, and mucosal healing, the sensitivity analyses described in Section 16.1.4 will be used.

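### The SAP replaces the protocol's responder-count tipping point with a delta shift without declaring the change, and gives three different answers on which key secondary endpoints receive it

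*SAP*

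**What the plan says.** Protocol 10.4 fixes both the method and its scope: "A tipping point analysis will be performed for the primary and key secondary endpoints by considering all possible combinations of the number of responders". Nonresponder counts are paired with these for the missing subjects of each arm, and the boundary between significant and non-significant combinations is shown graphically. Protocol 10.7.1 lists eight key secondary endpoints, so the commitment covers ten endpoints in all.

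SAP 16.1.4.2 reads: "A tipping point approach based on multiple imputation of values through Week 12 and Week 52 will be used with a specified adjustment". Its first step is the missing-at-random imputation of SAP 16.1.4.1. A random shift is then added to the imputed rectal bleeding (RB), stool frequency (SF) and endoscopic (ES) subscores, so that the expected combined shift equals delta. On etrasimod, delta "will take increasing values from 0 with increments of 1 (maximum MMS of 9"); on placebo it moves the other way, towards better scores. The heat map has delta values on both axes. A grid of responder counts appears nowhere in the SAP, and SAP 3.3 does not list the change.

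On coverage of the key secondary endpoints:
- The SAP 16.2 text gives the 16.1.4 sensitivity analyses to endoscopic improvement and symptomatic remission only.
- SAP Table 3 adds mucosal healing, but as "X (MI, MI-CR, and NRI + MI only"), which leaves out the tipping point. The sensitivity cells for corticosteroid-free and sustained clinical remission are blank.
- SAP 16.2.4 says "For the key secondary endpoints of endoscopic improvement, symptomatic remission, and mucosal healing, the sensitivity analyses described in Section 16.1.4 will be used", with no exception for the tipping point.
- SAP 16.2.2 carries the missing-data methods of 16.1.2 over to the key secondary endpoints, and 16.1.2 lists all four sensitivity analyses, the tipping point among them.

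**The concern.** Every binary efficacy endpoint counts a missing outcome as nonresponse. The tipping point is the check that asks how far that rule would have to be wrong, and in which arm, before the conclusion changes. Three things about the planned version are unsatisfactory.

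First, a method named in the protocol was exchanged for another without being declared, although SAP 3.3 records changes as small as a histology cut-off moving from below 3.1 to at or below 3.1.

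Second, the replacement depends on the imputation model, and SAP 16.1.4.1 allows that model to be modified after unblinding, with the changes described in the study report. A count grid does not use that model.

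Third, a programmer cannot tell from the SAP which key secondary endpoints get the analysis. If mucosal healing is included, as 16.2.4 says, the analysis is not fully specified: healing also requires a Geboes score below 2.0, and 16.1.4.2 shifts only RB, SF and ES.

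**Working it through.** **1. The plan's own figures.** SAP 7 gives 280 and 140 subjects and a one-sided 0.025 level. Exact enumeration of Fisher's test gives 92.8% power at Week 52 (23.5% v 10.0%; normal approximation 93.9%) against 93.4% stated, and 95.6% at Week 12 (18.5% v 6.0%; normal approximation 96.0%) against 96% stated. SAP 16.1.4.1 uses 40 imputations at a projected 50% dropout: relative efficiency = 1/(1 + 0.50/40) = 98.8%, matching the stated value of about 99%. These figures hold, and none depends on which tipping point is used.

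**2. Tipping-point coverage of the eight key secondary endpoints** (number of endpoints in brackets).

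| Source | Endoscopic improvement (2) | Symptomatic remission (2) | Mucosal healing (2) | Corticosteroid-free remission (1) | Sustained remission (1) | Total |
|---|---|---|---|---|---|---|
| Protocol 10.4 | yes | yes | yes | yes | yes | 8 |
| SAP 16.2 text | yes | yes | no | no | no | 4 |
| SAP Table 3 | yes | yes | no | no | no | 4 |
| SAP 16.2.4 | yes | yes | yes | no | no | 6 |
| SAP 16.2.2 via 16.1.2 | yes | yes | yes | yes | yes | 8 |

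For any sensitivity analysis at all, Table 3 covers 6 of 8. The 16.2 text also repeats section 16.1.4.4 (the COVID-19 hybrid imputation) for each key secondary endpoint under the label of primary and supplementary analyses. Read literally, this conflicts with the blank cells of Table 3. The intended reference is probably 16.1.5.

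**3. Where the primary analysis sits.** Let mE and mP be the numbers with a missing outcome.
- Protocol grid: cell (i, j) adds i responders on etrasimod (0 to mE) and j on placebo (0 to mP). Cell (0, 0) is the primary nonresponder analysis.
- SAP grid: cell (0, 0) is missing-at-random imputation. Moving along the placebo axis can only add placebo remitters. The primary analysis is on this grid only if imputation produces no placebo remitters among the missing.

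**4. What a count grid would report.** This is an illustration. It assumes all 420 subjects, the design rates already reached with every missing subject a nonresponder, and an unstratified test with z = (pE − pP)/√[p(1−p)(1/280 + 1/140)], where p is the pooled rate. The actual primary set, restricted to baseline MMS 5 to 9, may be smaller.
- Week 52, starting from 66/280 v 14/140: with j = 7, 23.6% v 15.0%, z = 2.04, p = 0.041; with j = 8, 23.6% v 15.7%, z = 1.87, p = 0.062.
- Week 12, starting from 52/280 v 8/140: with j = 7, 18.6% v 10.7%, z = 2.07, p = 0.038; with j = 8, 18.6% v 11.4%, z = 1.87, p = 0.061.

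Either primary endpoint would tip at 8 extra placebo responders (8/140 = 5.7%) with none added on etrasimod. That is a statement about subjects, measured from the primary analysis. A delta map reports a shift in score points from a different starting place.

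**5. Computing load.** The grid has (mE + 1)(mP + 1) cells. The documents do not give the missing fraction. Assuming it is equal in both arms: 5% gives 15 × 8 = 120, 10% gives 29 × 15 = 435, 20% gives 57 × 29 = 1,653, and 30% gives 85 × 43 = 3,655. Each cell is one stratified test with no imputation.

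**The case against.** Delta-adjusted imputation is a recognised tipping-point method, and the protocol leaves the full description of sensitivity analyses to the SAP. Both points stand, so the delta shift need not be removed. They do not excuse an undeclared substitution: the protocol had already named the method and the endpoints, and adding detail is not the same as replacing them.

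The count grid is not free of assumptions either. The test is stratified by three two-level factors, so the added responders must be placed in strata by some rule. This is correct, and the rule has to be written down.

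A reader might infer three stronger claims that the documents do not support.
- *The delta grid is too coarse to be informative.* The shift distribution is in Appendix 3, which is redacted. Suppose the SF and ES scores of imputed remitters are 0 or 1 equally often and baseline SF is at least 2. The share still in remission at delta 1 is then 46% if each component rises by 1 with probability delta/3, 33% if one point goes to a component chosen at random, and 57% if each component gets a uniform shift on 0 to 2·delta/3, rounded. At delta 3 the shares are 0%, 0% and 6%. The answer depends on the unseen code, and these figures leave out the placebo axis, which carries the result in step 4.
- *Half the outcomes will be missing.* The 50% is a dropout projection used to choose the number of imputations. SAP 16.1.2 treats exits for worsening, lack of efficacy or UC-related adverse events as known nonresponse, so the missing fraction is smaller by an amount the documents do not state.
- *The tipping point has been dropped for four key secondary endpoints.* That is one reading. Under 16.2.4 it would be two, and under 16.2.2 none. The established fault is contradiction. Corticosteroid-free and sustained remission also keep the mFAS as-observed and Per Protocol analyses, which the SAP labels supplementary.

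**Conclusion.** The point holds as an undeclared departure from protocol 10.4 combined with an internal contradiction over coverage. The tipping point reaches 4, 4, 6 or 8 of the eight key secondary endpoints according to where one looks in the SAP, against 8 in the protocol. As planned, the check is measured from missing-at-random imputation rather than from the nonresponder analysis it is meant to test.

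These conclusions rest on the text alone and need no assumption about the redacted code or the amount of missing data. The figure of 8 placebo responders is illustrative and rests on the assumptions stated with it. The primary analysis, type I error control and power are untouched, and the coprimary endpoints keep their other three sensitivity analyses. Whether the delta shift is the better or worse method is a matter of preference and is not part of the finding.

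**What to change.** 1. Add the protocol's responder-count grid to the SAP for both primary and all eight key secondary endpoints. Recompute the stratified test in each cell, plot the boundary, and mark (0, 0) as the primary analysis.
2. State one rule for allocating added responders to the randomisation strata, for example in proportion to the missing subjects in each stratum. Confirm that subjects classed as known nonresponders under SAP 16.1.2 stay outside the grid.
3. The delta-shift analysis may stay alongside the grid. If it is kept for mucosal healing, say how the Geboes score is handled.
4. Make the 16.2 text, Table 3, 16.2.2 and 16.2.4 name the same endpoints and methods, and check the 16.2 reference to 16.1.4.4.
5. List any remaining departure from protocol 10.4 in SAP 3.3.

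The cost is SAP wording and a short loop over counts. No new data and no further imputation are needed. The only downside is a little more programming and output.
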